**Table 3-1 Power for detecting a treatment difference between tropifexor + CVC and tropifexor and CVC monotherapy**

Assumed tropifexor response rate	Assumed response rate of tropifexor + CVC	Power N = 50/arm vs. tropifexor monotherapy	Power N = 50/arm vs. CVC monotherapy
Current target 42% response rate at Week 48 (50% improvement over OCA)	½ effect of CVC added to tropifexor ((60%)	48%	75%
	¾ effect of CVC added to tropifexor (69%)	81%	95%
	Full effect of CVC added to tropifexor (77%)	96%	99%
Response rate between target and OCA at Week 48 (35%)	½ effect of CVC added to tropifexor (53%)	48%	48%
	¾ effect of CVC added to tropifexor (62%)	81%	81%
	Full effect of CVC added to tropifexor (70%)	96%	96%
Worst case: tropifexor same effect as OCA 28% at Week 48	½ effect of CVC added to tropifexor (46%)	50%	23%
	¾ effect of CVC added to tropifexor (55%)	82%	56%
	Full effect of CVC added to tropifexor (63%)	96%	81%

\*Power calculated assuming a two-sided Type I error rate of 0.10

## 4 Change to protocol specified analyses

- AE and SAE summary by the onset time with respect to COVID-19 pandemic in different countries and regions are added.
- Paired-biopsy reading will be used for all biopsy-based outputs.
- NAS-based definition of resolution of steatohepatitis is added in the supportive analyses for secondary efficacy endpoint [REDACTED]

## 5 Appendix

### 5.1 Imputation rules

#### 5.1.1 Study drug

The date of the end-of-treatment visit (EOT, Week 48) will be used if the date of last administration of study treatment is missing and the date of randomization will be used if the date of first administration is missing.

#### 5.1.2 AE date imputation

##### Adverse Event Start Date Imputation (#IMPUTAEV)

This algorithm is expressed in the Variable Source Derivation column as #IMPUTAEV(*event*) where *event* is the partial start date of the adverse event.

The following table explains the notation used in the logic matrix. Please note that **missing start dates** will not be imputed.

	Day	Month	Year
Partial Adverse Event Start Date	Not used	MON	YYYY
Treatment Start Date	Not used	TRTM	TRTY

The following matrix explains the logic behind the imputation.

	MON MISSING	MON < TRTM	MON = TRTM	MON > TRTM
YYYY MISSING	NC Uncertain	NC Uncertain	NC Uncertain	NC Uncertain
YYYY < TRTY	(D) Before Treatment Start	(C) Before Treatment Start	(C) Before Treatment Start	(C) Before Treatment Start
YYYY = TRTY	(B) Uncertain	(C) Before Treatment Start	(B) Uncertain	(A) After Treatment Start
YYYY > TRTY	(E) After Treatment Start	(A) After Treatment Start	(A) After Treatment Start	(A) After Treatment Start

The following table is the legend to the logic matrix.

If AE end date is complete and AE end date < Treatment start date then AE start reference = min (informed consent date, earliest visit date from SV)

Else if AE end date is partial or AE is ongoing then AE start reference = treatment start date

Relationship	Date Imputation
Before AE Start reference	Partial date indicates AE start date prior to AE start reference
After AE Start reference	Partial date indicates AE start date after AE start reference
Uncertain	Partial date insufficient to determine relationship of AE start date to AE start reference
Imputation Calculation	
NC / Blank	No convention
(A)	01MONYYYY
(B)	Treatment start date+1
(C)	max(15MONYYYY, the start date of the screening period +1 day)
(D)	max(01JULYYYY, the start date of the screening period +1 day)
(E)	01JANYYYY
Complete date	No date imputation

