### **2.5 Analysis of the primary objective**

#### **2.5.1 Primary endpoint**

The primary study objective is to evaluate the safety and tolerability of tropifexor + CVC in patients with NASH and fibrosis (stage 2 or 3 as per NASH CRN histological score, F2/F3) by monitoring adverse events, vital signs and laboratory values during treatment as compared to monotherapy with each of tropifexor and CVC. The related endpoints are (over treatment):

- occurrence of adverse events,
- occurrence of serious adverse events,
- occurrence of adverse events resulting in discontinuation of study treatment,

- occurrence of adverse events of special interest,
- changes in vital signs and laboratory values.

Only treatment emergent adverse events will be considered for the analysis, which are defined as those starting on or after first day of application of study treatment and before EOS visit or 30 days after EOT visit, whichever comes earlier.

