### Adverse Event End Date Imputation

Imputed date = date part of original date, if complete date

If a patient is not randomized, then the AE end date is the date of completion of pre-randomization period.

If a patient is randomized:

If AE end date, month, and year are missing or just month is missing, then the AE end date is set to the study completion/discontinuation visit date.

If AE day is missing, then it is set to minimum of (treatment end day, last day of the month).

If imputed AE end date is less than the AE start date, use the AE start date as the imputed AE end date.

Impute Date Flag:

If year of the imputed date  $\diamond$  YYYY then date flag = Y

else if month of the imputed date  $\diamond$  MON then date flag = M

else if day of the imputed date  $\diamond$  day of original date then date\_flag = D

else date flag = null

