#### 5.1.3 Concomitant medication date imputation

This algorithm is used when *event* is the partial start date of the concomitant medication or non-drug therapy/procedure.

The following table explains the notation used in the logic matrix. Please note that **completely missing start dates** will not be imputed. Also note that imputation of a start date must not result in a date later than the end date. In such case, start date will be max(01-MMM-YYYY, Treatment start date) if only the day is missing and max(01-JAN-YYYY, Treatment start date) if day and month are missing.

	Day	Month	Year
Partial CMD Start Date	Not used	MON	YYYY
Treatment Start Date	Not used	TRTM	TRTY

The following matrix explains the logic behind the imputation.

	MON MISSING	MON < TRTM	MON = TRTM	MON > TRTM
YYYY MISSING	(C2) Uncertain	(C1) Uncertain	(C1) Uncertain	(C1) Uncertain
YYYY < TRTY	(D) Before Treatment Start	(A) Before Treatment Start	(A) Before Treatment Start	(A) Before Treatment Start
YYYY = TRTY	(C2) Uncertain	(A) Before Treatment Start	(C2) Uncertain	(B) After Treatment Start
YYYY > TRTY	(E) After Treatment Start	(B) After Treatment Start	(B) After Treatment Start	(B) After Treatment Start

The following table is the legend to the logic matrix.

Relationship	Date Imputation
Before Treatment Start	Partial date indicates CMD start date prior to Treatment Start Date
After Treatment Start	Partial date indicates CMD start date after Treatment Start Date
Uncertain	Partial date insufficient to determine relationship of CMD start date relative to Treatment Start Date
Imputation Calculation	
(A)	15MONYYYY
(B)	01MONYYYY
(C1 or C2)	IF relative reference start = before THEN Treatment Start Date -1 day ELSE IF relative reference start = '' THEN Treatment Start Date +1 day
(D)	01JULYYYY
(E)	01JANYYYY

Concomitant Medication End Date Imputation:

If not ongoing then

Imputed date = date part of CMENDTC, if complete date

Imputed date = min(reference end date, DEC 31) , if month is missing, (C2, D, E)

Imputed date = min(reference end date, last day of the Month) , if day is missing. (A, B, C1)

Concomitant Medication Date Flag:

If not a complete date then

Y - If year of the imputed date <> YYYY else

M - If month of the imputed date <> MON else

D

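### AE start-date imputation (SAP 5.1.2): some partial start dates are set to the day after first dose even when the recorded end date shows the event was over before dosing

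*SAP*

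**What the plan says.** SAP 5.1.2 imputes partial AE start dates from a matrix that compares the reported month and year with the month and year of treatment start. Two cells lead to formula (B): start year equal to the treatment year with the month missing, and start year and month both equal to those of treatment start. Formula (B) is "Treatment start date+1".

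The legend below the matrix introduces a different anchor for events that ended before first dose. The condition reads "If AE end date is complete and AE end date < Treatment start date then AE start reference", and the value it sets is "AE start reference = min (informed consent date, earliest visit date from SV"). It continues: "Else if AE end date is partial or AE is ongoing then AE start reference = treatment start date". The labels for before, after and uncertain are then explained relative to this reference, while the matrix cells and formula (B) still refer to treatment start.

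Three other rules bear on the result:

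- SAP 2.5.1 counts only treatment-emergent events, "which are defined as those starting on or after first day of application of study treatment". The definition in SAP 2.8.1 is also met by any start after the first dose.
- The AE end-date rule says: "If imputed AE end date is less than the AE start date, use the AE start date as the imputed AE end date".
- For concomitant medication, SAP 5.1.3 adds a guard: "imputation of a start date must not result in a date later than the end date". The AE start-date rules have no such guard.

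**The concern.** The SAP clearly means to treat events that ended before dosing separately, because it defines a consent-based reference for them. The formulas never use that reference. An event whose end date proves it was over before any drug was taken can therefore receive a start date after first dose.

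AE occurrence is a primary variable, and it is assessed descriptively without hypotheses (SAP 2.5.2), so the counts themselves are the evidence. AEs are recorded from consent (protocol 7.1). Screening lasts up to 10 weeks (protocol 3.1) and can include a liver biopsy, so pre-dose events in randomized patients are to be expected. Every misplaced event lands on Day 2, inside the first-4-weeks interval of the onset-time tables in SAP 2.8.1. The protocol plans no sensitivity analysis of the primary variables (9.4.4), and the supportive analyses in SAP 2.5.4 concern only COVID-19. No planned analysis would reveal the error.

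**Working it through.** The documents give no figure to reproduce. The check is to run the stated rules on dated examples and then enumerate them.

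**One illustrative patient.** Consent 25 Mar 2019, first dose 20 May 2019 (56 days later, within the 10-week screening limit). Three ways of applying the text are compared:

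- Reading 1: as written, with the matrix keyed to treatment start and (B) = treatment start + 1 day.
- Reading 2: matrix keyed to the AE start reference, (B) unchanged.
- Reading 3: matrix keyed to the reference and (B) = reference + 1 day. This is a repair; the text does not say it.

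| Reported start | Recorded end | Reading 1 | Reading 2 | Reading 3 |
|---|---|---|---|---|
| May 2019 | 12 May 2019 | (B): 21 May | (A): 1 May | (A): 1 May |
| Apr 2019 | 25 Apr 2019 | (C): 15 Apr | (A): 1 Apr | (A): 1 Apr |
| Mar 2019 | 30 Mar 2019 | (C): 26 Mar | (B): 21 May | (B): 26 Mar |
| 2019 only | 12 May 2019 | (B): 21 May | (B): 21 May | (B): 26 Mar |

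Under Reading 1 the first event starts 21 − 12 = 9 days after it ended. A start of 21 May meets both treatment-emergent definitions. Reading 2 corrects that event but misplaces the one in the consent month, and the year-only date is wrong under both readings.

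**Partial end date, same patient.** Start 2019 only, end April 2019 with the day missing. The latest possible end is 30 April, before first dose. Because the end date is partial, the legend makes treatment start the reference, so all three readings put the event on 21 May. Changing (B) alone does not repair this case.

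**Enumeration.** Assumptions: each first-dose day of 2019; consent 70 days earlier; an event starting on each screening day; durations of 1, 3, 7 and 14 days; only events that ended before first dose, with complete end dates. Per first-dose day this gives 69 + 67 + 63 + 56 = 255 events, and 255 × 365 = 93,075 in all. Share classed as treatment-emergent:

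| Missing part of start date | Reading 1 | Reading 2 | Reading 3 |
|---|---|---|---|
| Day | 14,047 / 93,075 = 15.1% | 22,952 / 93,075 = 24.7% | 0% |
| Day and month | 83,275 / 93,075 = 89.5% | 85,025 / 93,075 = 91.4% | 0% |

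Every misclassified event comes from cell (B). The percentages are conditional on a partial start date and on the assumed durations. They describe the rule and do not estimate a rate for the trial.

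**Size per patient.** 1/50 = 2 percentage points of an arm, as SAP 3.1 itself notes. With the 193 patients reported as randomized in protocol Amendment 3, an arm averages 193/4 = 48.25, and one patient is 1/48.25 = 2.1 points.

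**Effect on contrasts.** If k misplaced patients are added to each of two arms of 50, the risk difference is (x1 + k)/50 − (x0 + k)/50 = (x1 − x0)/50, which is unchanged. A risk ratio moves towards 1. Unequal additions add noise.

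**The case against.** The strongest defence is that this is a drafting conflict with the safeguard already on the page. The legend shows the intent, and a programmer who followed it could key the matrix to the reference. That stands in part: doing so dates the May event correctly, and in general rescues dated months after the consent month. It does not rescue consent-month or year-only starts, because (B) still points to the day after treatment start.

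The second defence is that few events can qualify. The start must be partial and must reach (B). Complete start dates are not imputed, and cells (C) and (D) keep events before treatment. Pre-consent conditions go to medical history (protocol 6.2.2), and missing values are queried (protocol 8.3). All of this stands and limits the reach of the point.

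A reader might also infer more than the documents support:

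- *That the error adds several points to AE rates.* No count of partial dates is given. A patient adds to a term only if the same term did not also occur on treatment. The overall any-AE line has little room to move if incidence is like that of the cited CVC phase 2b study, at least 95% in each group.
- *That it dilutes the comparison of combination with monotherapy.* The rule is identical across arms, and equal additions leave risk differences unchanged.
- *That events with no start year drop out.* The SAP says "Please note that missing start dates will not be imputed" and gives no convention for a missing year. How such events are classed is not stated; exclusion is not shown.
- *That a complete reported end date is certainly overwritten.* The end-date section keeps a complete date, but labels it an imputed date and then applies "If imputed AE end date is less than the AE start date, use the AE start date as the imputed AE end date". Whether that last rule reaches a complete date is ambiguous.

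**Conclusion.** The rule is wrong as written, within a narrow scope. An AE whose partial start date falls in cell (B) is imputed to the day after first dose even when its recorded end date precedes first dose, and it then counts as treatment-emergent in the primary safety tables. Reading the matrix against the reference date reduces some cases and creates others, so the text needs correcting.

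The number of affected events is unknown from the documents. The size that can be stated is about 2 percentage points of an arm per affected patient, for a term that the patient did not also have on treatment. No direction of bias between arms is shown. Assigning truly uncertain events to the treatment period is a reasonable conservative choice. These events are not uncertain, because the end date settles the matter. Given how little the correction costs, it should be made.

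**What to change.** In SAP 5.1.2:

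1. Put one condition ahead of the matrix. If the AE end date (complete, or the latest date compatible with a partial end date) is before first dose, the AE is pre-treatment. Impute its start as max(first day of the reported month or year, consent date), never later than the end date. For the illustrative patient this gives 1 May, 1 April, 25 March and 25 March for the four tabulated events, and 25 March for the event with the partial end date. All precede both the event's end and first dose.
2. Use (B) only when the end date is on or after first dose, cannot be shown to precede it, is missing, or the AE is ongoing.
3. State that an imputed AE start may not be later than a recorded end date, as SAP 5.1.3 already does for concomitant medication.
4. State that the end-date rule may not change a complete reported end date.

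The AE start reference can then be removed, or kept only where a formula uses it. The cost is SAP wording, one programming condition and one date check. No new data are needed, and the conservative handling of truly uncertain events is kept.

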### Adverse Event End Date Imputation

Imputed date = date part of original date, if complete date

If a patient is not randomized, then the AE end date is the date of completion of pre-randomization period.

If a patient is randomized:

If AE end date, month, and year are missing or just month is missing, then the AE end date is set to the study completion/discontinuation visit date.

If AE day is missing, then it is set to minimum of (treatment end day, last day of the month).

If imputed AE end date is less than the AE start date, use the AE start date as the imputed AE end date.

Impute Date Flag:

If year of the imputed date  $\diamond$  YYYY then date flag = Y

else if month of the imputed date  $\diamond$  MON then date flag = M

else if day of the imputed date  $\diamond$  day of original date then date\_flag = D

else date flag = null

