**Table 2-3 Defined Dates**

Region/Country	Start Date	End Date
Italy	23-Feb-2020	End date has not yet been defined
Rest of the World	01-Mar-2020	End date has not yet been defined

Tabulations of adverse events, SAE, and adverse events of special interest broken down by time of onset according to the following intervals will be provided as well:

- Starting within 4 weeks after first administration of study treatment,
- Starting between 4 weeks and 12 weeks after first administration of study treatment,
- Starting more than 12 weeks after first administration of study treatment.

*For the legal requirements of ClinicalTrials.gov and EudraCT, two required tables on treatment emergent adverse events which are not serious adverse events with an incidence greater than or equal to 5% in any treatment group and on treatment emergent serious adverse events and SAE suspected to be related to study treatment will be provided by system organ class and preferred term on the safety set population.*

*If for a same patient, several consecutive AEs (irrespective of study treatment causality, seriousness and severity) occurred with the same SOC and PT:*

- *a single occurrence will be counted if there is  $\leq 1$  day gap between the end date of the preceding AE and the start date of the consecutive AE*
- *more than one occurrence will be counted if there is  $> 1$  day gap between the end date of the preceding AE and the start date of the consecutive AE*

*For occurrence, the presence of at least one SAE / SAE suspected to be related to study treatment / non SAE has to be checked in a block e.g., among AE's in a  $\leq 1$  day gap block, if at least one SAE is occurring, then one occurrence is calculated for that SAE.*

*The number of deaths resulting from SAEs suspected to be related to study treatment and SAEs irrespective of study treatment relationship will be provided by SOC and PT.*

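### SAP 5.1.2 moves an AE end date with a known year but missing month to the end-of-study visit, so the imputed date can contradict the recorded year and may merge a next-year recurrence in the registry tables

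*SAP*

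**What the plan says.** For randomized patients, SAP 5.1.2 handles two situations together. A wholly missing end date and one with an unknown month both go to the end of the study: "or just month is missing, then the AE end date is set to the study completion/discontinuation visit date". The section's only bound on the result is a lower one: "If imputed AE end date is less than the AE start date, use the AE start date as the imputed AE end date". A flag step, opening "If year of the imputed date", assigns Y when the imputed year differs from the reported year.

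SAP 5.1.3, on concomitant medication end dates, treats an unknown month differently: "Imputed date = min(reference end date, DEC 31) , if month is missing, (C2, D, E".

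Imputed AE end dates could affect a planned output through the occurrence rule in SAP 2.8.1. That rule belongs to the text introduced by "For the legal requirements of ClinicalTrials.gov and EudraCT, two required tables on treatment emergent adverse events". For one patient and consecutive AEs with the same SOC and preferred term, "a single occurrence will be counted if there is" a gap of at most 1 day. The gap is the "day gap between the end date of the preceding AE and the start date of the consecutive AE". A longer gap gives more than one occurrence.

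**The concern.** An imputation rule for a partial date should respect the part that was recorded. This one discards a known year. Protocol 7.1 asks sites to report an ongoing event with an outcome of not recovered/not resolved, so a reported end year indicates that the event ended in that year. Moving its end into the next year puts a date in the analysis data that the site's entry rules out.

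The neighbouring medication rule respects the year for the same pattern of missingness, and the SAP gives no reason for the difference.

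At stake is the count of occurrences in the two registry tables. If a term recurs in the following year, the recurrence may start inside the stretched first event and be counted as part of it.

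**Working it through.** The documents give no figure on this point, so there is none to reproduce. The check applies the written rules to calendar dates.

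**Inputs from the SAP**
- Treatment of 48 weeks plus 4 weeks of follow-up (SAP 1.1): Day 1 to end of study is 52 × 7 = 364 days.
- AE end-date rule and its lower bound (5.1.2), medication cap (5.1.3), one-day gap rule (2.8.1).

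**Assumed for illustration:** first dose 2 July 2019, AE end reported as 2019 with month unknown, same SOC and preferred term recurring on 15 February 2020.

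**Which branch applies.** The missing-day rule in 5.1.2 needs a month, because it uses the last day of that month. A year-only date can therefore only fall under the month-missing branch. If that branch is read narrowly, as day and year known, the year is still on record.

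**Step 1, completion date.** 2 July 2019 + 364 days = 30 June 2020.

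**Step 2, rule as written.** The end date becomes 30 June 2020. Days past 31 December 2019: 31 + 29 + 31 + 30 + 31 + 30 = 182. The flag is set to Y, but the date stands.

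**Step 3, with the year respected as in 5.1.3.** The earlier of 30 June 2020 and 31 December 2019 is 31 December 2019.

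**Step 4, gap rule.**

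| End date used | Gap to 15 Feb 2020 | Occurrences |
|---|---|---|
| 30 June 2020 (as written) | −(14 + 31 + 30 + 31 + 30) = −136 days | 1 |
| 31 Dec 2019 (capped) | 31 + 15 = 46 days | 2 |

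**Step 5, range of the shift.** Take an end year equal to the first-dose year and a 364-day span. In a 365-day year, a first dose on 1 January gives completion on 31 December, so there is no shift. A first dose on 2 January gives 1 day, and one on 31 December gives 364 days. Completion falls in a later calendar year for 364 of 365 possible first-dose dates (364 of 366 in a leap year). A COVID-19 treatment extension would lengthen the span and raise the upper end; early discontinuation would shorten it.

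**Step 6, control.** If the reported end year is the completion year (2020 here), both rules give 30 June 2020 and there is no discrepancy.

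**The case against.** The case for leaving the rule alone is that it hardly touches the results. Much of that stands:

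- The main AE summaries in SAP 2.8.1 count patients. Treatment-emergent status and the COVID-19 and time-of-onset tables rest on the start date. None of these changes.
- The SAP does not state that imputed end dates enter the gap rule. This is an inference: without imputation, a partial date gives no gap to compute.
- The flag makes the changed year visible in the data, though it does not prevent the change.
- Protocol 7.1 requires AE start and end dates and Protocol 8.3 provides for queries on missing values, so year-only end dates should be uncommon.
- The medication rule is not a perfect model. Its C2 category also covers a missing year, where 31 December has no year to attach to. For a known year it works.

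Two stronger readings are tempting, and the documents support neither.

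First, a reader might infer that the stretched event absorbs every later recurrence of the term. The gap rule compares only the preceding event with the next one. Suppose a second event runs from 15 to 20 February 2020 and a third starts on 1 April 2020. The third is compared with the second, the gap is 9 + 31 + 1 = 41 days, and it counts separately. Full absorption would need a running latest end date for the block, which the SAP does not describe.

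Second, a reader might infer that resolved events would appear ongoing. Outcome is a separate item on the AE form (Protocol 7.1), and SAP 2.8.1 describes no output on AE duration or time to resolution.

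**Conclusion.** The rule is wrong as written, but the point is minor. SAP 5.1.2 replaces a recorded end year whenever that year precedes the year of the completion or discontinuation visit, and it is inconsistent with SAP 5.1.3. For an end reported in the first-dose year and a 52-week span, the imputed date is 1 to 364 days too late relative to 31 December of that year.

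The reach into planned output is narrow. It needs a year-only end date in an earlier year, a next-year recurrence in the same patient with the same SOC and preferred term, and use of imputed dates in the gap rule. Where all three hold, the merge can only lower the occurrence count in the two registry tables. The documents do not say how many such dates exist; the number is probably small. The 2019 and 2020 dates above are assumptions chosen to show the mechanism.

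**What to change.** In SAP 5.1.2, separate the two cases:

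- **Year known, month missing:** AE end date = min(study completion/discontinuation visit date, 31-DEC-YYYY), not earlier than the AE start date.
- **End date fully missing:** keep the present rule.

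It would also help to state in SAP 2.8.1 whether the gap rule uses imputed end dates.

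The cost is one line of SAP text and one of derivation code, plus a sentence for the clarification. No new data are needed and the patient-level AE summaries do not change. The corrected rule still places the end as late as the record allows, so a recurrence within the reported year may still merge with the first event. The change removes the contradiction with the recorded year, not all late-end bias.

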### 1.1 Study design

This study is a 48-week, randomized, double-blind, multicenter study that consists of a screening period, a treatment period starting from randomization on Day 1 and running to Week 48, and a follow up period of 4 weeks after the last dose of study treatment. The total study duration is up to 60 weeks.

The study population are adult male and female patients with histologic evidence of NASH and fibrosis (stage 2 or 3 as per NASH CRN histological score, F2/F3); see Inclusion and Exclusion criteria in the protocol for details.

At baseline, approximately 200 patients whose eligibility is confirmed will be randomized in a 1:1:1:1 ratio, resulting in approximately 50 patients randomized in each of the four arms:

**Arm A:** tropifexor 140 µg, once-daily

**Arm B:** CVC 150 mg, once-daily

**Arm C:** tropifexor 140 µg + CVC 150 mg, once-daily

**Arm D:** tropifexor 90 µg + CVC 150 mg, once-daily.

The primary analysis will be performed when all randomized patients have completed or discontinued the trial participation. No interim analyses are planned.

Due to the COVID-19 pandemic, it may not be possible for patients to return in time for the Week-48 visit to perform scheduled assessments including biopsies, and according to drug dispensing plan in Section 5.5.2 of the protocol, the Week-48 visit and associated assessments can be delayed up to approximately 12 weeks. Since the primary objective of the study is to determine if there is a safe combination between one of the chosen doses of tropifexor and 150 mg of cenicriviroc, all assessment results obtained, including those from eligible patients after Week 48, will be included in analyses as they are with no special plan to account for the treatment extension.

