### 2.8.1 Adverse events (AEs)

Treatment emergent adverse events (events started after the first dose of study treatment or events present prior to the first dose of study treatment but increased in severity based on preferred term, until EOS visit or 30 days after EOT visit, whichever comes earlier) will be summarized. AEs will be summarized by presenting, for each treatment group, the number and percentage of patients having experienced

- Any adverse event (AE),
- Any serious adverse event (SAE),
- Any adverse event by primary system organ class (SOC),
- Any adverse event by preferred term (PT),
- Any adverse event by severity,
- Any adverse event possibly related to study treatment (investigator assessment),
- Any adverse event resulting in discontinuation of study treatment,
- Any adverse events of special interest for tropifexor or CVC treatment,
- Any adverse events by onset time before and after the start date of COVID-19 pandemic by country/region,
- Any serious adverse events by onset time before and after the start date of COVID-19 pandemic by country/region.

If a patient reported more than one adverse event with the same preferred term, the adverse event with the greatest severity will be presented. If a patient reported more than one adverse event within the same primary system organ class, the patient will be counted only once with the greatest severity at the system organ class level, where applicable.

The start date of COVID-19 for different countries or regions is defined in Table 5-1 of “COVID-19 (Coronavirus) Guidance - Start and End Dates by Region for Sensitivity Analyses” Version 1.0 released on May 19, 2020. As of the time of finalization of this SAP, the start (and end) dates are listed below:

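### The AE end-date rule for a missing day can override the reported month and so inflate the registry occurrence counts

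*SAP*

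**What the plan says.** SAP 5.1.2, under Adverse Event End Date Imputation, gives three rules for randomized patients.

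- Only the day is missing: "If AE day is missing, then it is set to minimum of (treatment end day, last day of the month".
- The whole date or the month is missing: "then the AE end date is set to the study completion/discontinuation visit date".
- Lower bound: "If imputed AE end date is less than the AE start date, use the AE start date as the imputed AE end date". There is no lower bound at the first day of the reported month.

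An imputation flag follows. One branch begins "else if month of the imputed date" and marks a month that differs from the reported one. It records the discrepancy but does not prevent it.

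Two other parts of SAP 2.8.1 matter. Treatment-emergent events are collected "until EOS visit or 30 days after EOT visit, whichever comes earlier". For the registry tables, consecutive records of the same SOC and PT in one patient are merged if the gap is at most 1 day. Otherwise "more than one occurrence will be counted if there is" more than a 1 "day gap between the end date of the preceding AE and the start date of the consecutive AE".

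**The concern.** Adverse events often end after treatment ends. SAP 1.1 describes "a follow up period of 4 weeks after the last dose of study treatment". Protocol 7.1 requires each event to be followed until it has resolved or is considered permanent. Protocol section 6 follows medically important drug-related events beyond the end-of-study visit. End months later than the treatment-end month are therefore expected, and the rule handles them badly.

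The site has reported a month, and the imputation overrides it. The rule also ranks information the wrong way round: a record with no end date at all goes to the later study completion visit, while a record with a known month and year is pulled back to treatment end.

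At stake are the occurrence counts in the two registry tables, because the gap rule uses the end date of the preceding record. Safety is the primary objective, so these tables should follow the reported data.

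**Working it through.** The plan states no figure on this point, so there is none to reproduce. The check applies the rule as written and then the gap rule. All dates below are assumed.

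**General result.** Let T be treatment end, S the AE start, and M the reported end month.

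- Rule as written: end = max( min(T, last day of M), S ).
- If M is later than the month of T, then T is earlier than every day of M, so the minimum is always T.
- If S ≤ T, the end becomes T, outside the reported month.
- If S > T, the end becomes S and the event lasts 1 day. This contradicts M unless the event also began in M.

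**Example A: event begins on treatment.** T = 20 January 2020; end of study = T + 28 days = 17 February 2020; S = 10 January; end reported as February 2020, day missing.

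- Rule as written: min(20 January, 29 February) = 20 January; duration 11 days.
- Shortest duration consistent with the report: 10 January to 1 February = 23 days.
- End date wholly missing instead: 17 February, 39 days.

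Now add a second record with the same SOC and PT, starting 1 February.

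- Any end date in February: gap of 0 days or less, so 1 occurrence.
- Rule as written: 1 February − 20 January = 12 days, more than 1, so 2 occurrences.

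**Example B: event begins after treatment.** Same T, S = 27 January, end reported as February.

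- The minimum is 20 January, before S, so the end is reset to 27 January; duration 1 day.
- Shortest duration consistent with the report: 27 January to 1 February = 6 days.
- Second record on 1 February: rule gap 5 days, so 2 occurrences; any February end date gives 1.

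**How often the months differ.** Take every possible treatment-end date in 2020 and each of the 28 days that follow. In each of the 12 months, the days falling in a later calendar month sum to 1 + 2 + … + 28 = 406. The share is 12 × 406 / (366 × 28) = 4,872 / 10,248 = 47.5%. For a 30-day window it is 50.8%. This describes the calendar only. The documents do not give the number of AE records that lack an end day.

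**What does not move.** Treatment-emergent status depends on onset or worsening. The patient counts and percentages in SAP 2.8.1, including those by severity, relationship and seriousness, do not use the end date. Start-date imputation in SAP 5.1.2 compares the end date with treatment start only when the end date is complete.

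**The case against.** The strongest reply concerns wording. The sentence says *day*, not *date*, and its grammatical subject is the missing day. On that reading, Example A gives min(20, 29) = 20, so 20 February, and the reported month is kept. This reading is possible, and it shows that the line is ambiguous. It is the less likely one. The parallel rule for concomitant medications in SAP 5.1.3 uses the same minimum with a full reference end date, and the day number on which treatment stopped says nothing about an event that ended in another month. The flag does not settle the matter, since it could also fire when the month is missing.

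A second reply is that two occurrences may be right. Suppose the second record in Example A starts on 10 February. The rule then gives a gap of 21 days, but a true end from 1 to 8 February would also leave a gap of more than 1 day. This stands for that date: the count is uncertain and the rule is not shown to be wrong. It does not apply when the second record starts on 1 February, where every consistent end date gives one occurrence.

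A reader might also infer four stronger points that the documents do not support.

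- *That conclusions on reversibility are distorted.* No planned summary of AE duration or time to resolution is visible, and outcome is recorded separately (Protocol 7.1).
- *That a single continuing event is split.* One record has no consecutive record, so it cannot be split.
- *That events appear to end before treatment end.* When the reported month is later, the imputed date is treatment end itself or the later AE start.
- *That the error reaches about 48 weeks in early stoppers.* This needs follow-up to Week 52 (Protocol 5.6.2 and section 6). Protocol 5.6.1 instead places the follow-up visit 4 weeks after last treatment, and SAP 1.1 also gives 4 weeks. The longer figure cannot be relied on.

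**Conclusion.** On the likelier reading, the rule is wrong as written: it replaces a reported month with an earlier date whenever an event that began on treatment ended in a later calendar month. It also shortens to one day any event that began after treatment and ended in a later month.

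The practical effect is small. It is confined, in the visible plan, to occurrence counts in the ClinicalTrials.gov and EudraCT tables. It also needs a particular pattern: two consecutive records with the same SOC and PT, the first lacking only its end day, with an end month after the treatment-end month. Few records are likely to meet this, though the documents give no count. The main safety tables and their interpretation stand.

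The conclusion assumes that the cap is a date. If a day number was intended, the reported month survives and only the wording needs repair.

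**What to change.** Replace the missing-day rule with:

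end = max( min(study completion or discontinuation date, last day of reported month), first day of reported month, AE start date ).

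State every term as a date. In Example A this gives 17 February, so a second record on 1 February counts as the same occurrence. It also agrees with the date the SAP already uses when the month is missing.

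The lower bound at the first day of the month is needed because some events are followed past the end-of-study visit. With study completion on 17 February and a reported end in March, the cap alone would again give a date before the reported month; the bound gives 1 March.

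The cost is one SAP line and one line of code. There is a small downside: imputing late in the month can occasionally merge two occurrences that were truly separate, as could happen with the second record on 10 February.
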